10.4 Determination of sample size

Part 1 (CHICO)

This study uses historical controls estimated from cure rates presented in two publications [15][16]. The historical cure rates are as follows.

Publication	Age range	Sero-conversion rate (95%CI) in placebo patients
Andrade et al 1996	7-12	3/65 = 5% (1%,13%)
Sosa et al 1998	6 -12	2/44= 5% (1%,16%)

For the primary objective, superiority over placebo will be confirmed if the lower limit of the 95% CI for the nifurtimox (60-day regimen) cure rate is greater than 16%, the larger of the upper limits of the 95% CIs from the two publications.¹⁹⁴

According to Guhl et al [32], nifurtimox 12 month post treatment cure rate is about 55%, with a sample size of 200 for the 60-day regimen, the power is 99% for the lower limit of the 95% CI to be greater than 16%.¹⁹⁵

The number of subjects in the 30-day treatment regimen is based on the width of a 95% CI for the difference of two proportions. A sample size of 100 subjects for the 30-day subjects together with 200 subjects for the 60-day subjects will produce a CI with a half-width of approximately 0.12.

Part 2 (CHICO SECURE)

¹⁹⁴ Modified as per amendment 2

¹⁹⁵ Modified as per amendment 2

	Integrated Clinical Study Protocol BAY A2502/16027
03 NOV 2020	Version 11.0

Page: 84 of 259

According to Sosa-Estani [15, 35], the 48 months post treatment cure rate for benznidazole is about 5% as confirmed by two types of assay. For the primary objective, assuming a drop-out rate of 15%, the expected number of patients to be observed at the end of Part 2 (i.e., 48 months post treatment) in the 60-day regimen would be 170 out of the 200 patients in Part 1. Using the assumptions of 170 nifurtimox 60-day regimen patients in Part 2, a 5% cure rate, and that seronegative conversion events follow Poisson distribution, the estimated incidence rate is calculated to be 1.32% and the 95% CI of the incidence rate is (0.61%, 1.51%).

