03 NOV 2020

Version 11.0

Page: 212 of 259

Section # and name	Description of change	Brief rationale
Synopsis Section 5 Study design	Provided detailed study design for the LTFU	To satisfy FDA's request to "further describe and verify the clinical benefit of nifurtimox", and to implement
Synopsis Section 6.1 Inclusion criteria Section 6.2 Exclusion criteria	Provided selection criteria for the LTFU	FDA's recommendations to the detailed study concept for the LTFU
Synopsis Section 9.1 Tabular schedule of evaluations Section 9.2 Visit description	Provided the schedule of procedures/assessments and the detailed visits description for the LTFU	
Section 9.4 Efficacy	Provided efficacy assessments for the LTFU	
Section 9.6 Safety	Provided safety assessments for the LTFU	
Synopsis Section 10 Statistical methods and determination of sample size	Provided analysis sets, variables, statistical and analytical plan for the LTFU; Provided updated information on sample size	To satisfy FDA's request to "further describe and verify the clinical benefit of nifurtimox", and to implement FDA's recommendations to the detailed study concept for the LTFU; Sample size recalculation based on clarification of study objective in Amendment 2
Section 16.2 Form for interim phone contacts	Provided phone contact form for phone assessments in the LTFU	To satisfy FDA's request to "further describe and verify the clinical benefit of nifurtimox", and to implement FDA's recommendations to the detailed study concept for the LTFU

Typographical, grammatical, and other minor edits are not identified.

15.8 Amendment 8

Integrated protocol version 9.0, dated 23 JUL 2019.

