## 1. Introduction

This statistical analysis plan (SAP) describes the study objectives, study design, study population, efficacy and safety variables, statistical analysis methods, and study tables to be used in this study. The original protocol, Version 1.0, is dated 04 NOV 2014. This SAP v3.0, dated 26 JAN 2020, is based on the integrated clinical study protocol Version 11.0, dated 03 NOV 2020, which includes the CHICO SECURE part of the study.

This study consists of two parts:

- Part 1 comprises the treatment with nifurtimox including the 1-year follow up (CHICO)
- Part 2 comprises the 3-year long-term follow-up (LTFU) of all subjects who were randomized and received at least one dose of their assigned nifurtimox treatment regimen in CHICO (CHICO SECURE)

Part 1 (CHICO) was designed to develop a better understanding of the efficacy, safety/tolerability, and pharmacokinetics (PK) of nifurtimox in children with a diagnosis of Chagas' disease using pediatric formulations. Results from this study will demonstrate parasitological cure using conventional serological results to allow optimization of treatment of Chagas' disease in this most vulnerable population. In turn, this will improve the outlook for children by reducing mortality and long-term complications. This knowledge will allow for better and more appropriate approaches to the treatment of Chagas' disease. It will also provide more up-to-date information on the use of nifurtimox, and has the potential to increase our understanding of treatment response in children.

Part 2 (CHICO SECURE) was designed, at the request of the US Food and Drug Administration (FDA), to assess the incidence of seronegative conversion in subjects who were randomized and received at least one dose of their assigned 60- or 30-day nifurtimox treatment regimen. In part 2 (CHICO SECURE), subjects will be followed up for 3 years totaling to a follow-up period of 4 years after end of nifurtimox treatment, the first year of follow up is included in the design of part 1 (CHICO).

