## 3. Study Design

## 3.1 Part 1 (CHICO)

## **Design overview**

#### BAY No. A2502/IMPACT No. 16027 Page: 7 of 30

This is a Phase 3, prospective, randomized (to dosing regimen), age-stratified, double-blind, parallel-group study to evaluate the efficacy, safety/tolerability, and PK of oral administration of nifurtimox in children with a diagnosis of Chagas' disease. A schematic of the study design is presented in Figure 3-1.

#### Figure 3–1. Study Design of Part 1

D = Day, EOT = end-of-treatment, V = Visit.

a At Visits 4, 5, and 7, study site personnel will contact the subject/legally authorized representative via telephone to assess for the occurrence of AEs, use of concomitant medications, and compliance with study drug administration. If any safety concern arises, subjects may return to the study site for an Unscheduled Visit.
b Subjects who discontinue prematurely from study drug administration will continue to return to the investigational site for study assessments at Visits 3, 6, and 8 (EOT), and undergo telephone assessments as described for Visits 4, 5, and 7. If subjects are unable/unwilling to do so, they must return to the investigational site 30 (±3) days after the last dose of study drug for EOT (Visit 8) assessments, and undergo telephone assessments as described for Visits 4, 5, and 7. If the subject is unable/unwilling to return to the clinic for the EOT Visit 8), then a telephone assessment as described for Visits 4, 5, and 7. If subjects is unable/unwilling to return to the clinic for the EOT Visit 8), then a telephone

assessment as described for Visits 4, 5, and 7 may be performed in lieu of Visit 8 assessments.

In this study, approximately 300 pediatric subjects will be randomized (2:1 randomization, 60-day regimen vs. 30-day regimen). Subjects will be stratified by age at randomization into four strata as specified below:

- Stratum 1: 0 to 27 days
- Stratum 2: 28 days to younger than 8 months
- Stratum 3: 8 months to younger than 2 years
- Stratum 4: 2 years to younger than 18 years

A minimum of 38 subjects in each age stratum is targeted, but not required, in order to be able to derive meaningful safety conclusions. Enrollment will continue until this specification is

met, unless it is determined that such a target would be unlikely to be reached in a reasonable time.

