#### Secondary analysis of the primary efficacy variable

A secondary analysis will be done to compare the proportion of subjects with sero-reduction or sero-conversion for the 60-day and 30-day nifurtimox regimens. This will be performed using an asymptotic 2-sided 95% CI for the difference of two independent proportions.

The null hypothesis  $H_0$  is  $p_{nifurtimox, 60d} = p_{nifurtimox, 30d}$ 

The alternative hypothesis H1 is  $p_{nifurtimox, 60d} \neq p_{nifurtimox, 30d}$ , where  $p_t$  is the cure rate for treatment *t*.

Difference in efficacy between the two groups will be confirmed if the CI for the difference of two proportions of nifurtimox subjects (60-day regimen *versus* 30-day regimen) with sero-reduction or sero-conversion does not include 0. The proportions and asymptotic 2-sided limits ( $l_l$ ,  $l_u$ ) of the 95% CI for *pnifurtimox*, 60d - *pnifurtimox*, 30d can be obtained by [3]

$$\begin{split} \hat{p}_{i} &= \frac{x_{i}}{n_{i}}, \qquad i = 1, 2. \\ l_{u} &= (\hat{p}_{1} - \hat{p}_{2}) + 1.96\sqrt{(\hat{p}_{1}(1 - \hat{p}_{1})/n_{1}) + (\hat{p}_{2}(1 - \hat{p}_{2})/n_{2})} + \frac{1}{2} \left(\frac{1}{n_{1}} + \frac{1}{n_{2}}\right) \\ l_{l} &= (\hat{p}_{1} - \hat{p}_{2}) - 1.96\sqrt{(\hat{p}_{1}(1 - \hat{p}_{1})/n_{1}) + (\hat{p}_{2}(1 - \hat{p}_{2})/n_{2})} - \frac{1}{2} \left(\frac{1}{n_{1}} + \frac{1}{n_{2}}\right) \end{split}$$

where  $p_i$ ,  $x_i$  and  $n_i$  denote the cure rate, the number of nifurtimox subjects with sero-reduction or sero-conversion, and the total number of subjects, for treatment *i* respectively. Treatment *i*=1, 2 represents 60-day and 30-day nifurtimox regimens, respectively.

The SAS code will be:

*Reference Number: BPD-SOP-060 Supplement Version: 6* 

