## 6.5 Determination of sample size

## Part 1 (CHICO)

According to Guhl et al. [5], nifurtimox 12 months post-treatment cure rate is about 55%, with a sample size of 260 for the 60-day regimen, the power is 99% for the lower limit of the 95% CI to be greater than 16%.

The number of subjects in the 30-day treatment regimen is based on the width of a 95% CI for the difference of two proportions. A sample size of 130 subjects for the 30-day subjects together with 260 subjects for the 60-day subjects will produce a CI with a width of approximately 20%.

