## Part 2 (CHICO SECURE)

According to Sosa-Estani [7, 7], the 48 months post treatment cure rate for benznidazole is about 5% as confirmed by two types of assay. For the primary objective, assuming a drop-out rate of 15%, the expected number of patients to be observed at the end of Part 2 (i.e. 48 months post treatment) in the 60-day regimen would be 170 out of the 200 patients in Part 1. Using the assumptions of 170 nifurtimox 60-day regimen patients in Part 2, a 5% cure rate, and that seronegative conversion events follow Poisson distribution, the estimated incidence rate is calculated to be 1.32% and the 95% CI of the incidence rate is (0.61%, 1.51%).

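### SAP 6.5 Part 1 still sizes the study at 260/130 with a CI about 20% wide, although the rest of the SAP and protocol 10.4 describe about 300 subjects (200/100)

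*SAP*

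**What the plan says.** **SAP 6.5, Part 1.** The power sentence reads "with a sample size of 260 for the 60-day regimen, the power is 99" per cent, for the lower 95% limit to exceed 16% at a true cure rate of about 55%. The 30-day arm is then sized on CI width alone: "A sample size of 130 subjects for the 30-day subjects together with 260 subjects for the 60-day subjects will produce a CI". The full width is put at about 20%.

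**SAP 3.1, Design overview.** "approximately 300 pediatric subjects will be randomized (2:1 randomization", 60-day versus 30-day.

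**SAP 6.5, Part 2.** After 15% dropout, the number expected in the 60-day regimen at the end of Part 2 "would be 170 out of the 200 patients in Part 1".

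**Protocol 10.4.** "A sample size of 100 subjects for the 30-day subjects together with 200 subjects for the 60-day subjects will produce a CI". Its half-width is put at about 0.12. The power sentence there uses 200.

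**How the two documents are linked.** The SAP Introduction says that it "is based on the integrated clinical study protocol Version 11.0, dated 03 NOV 2020". Protocol 15.7.1 (Amendment 7) records a "Sample size recalculation based on clarification of study objective in Amendment 2".

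**Interval to be used.** SAP 6.2.1.1 compares the regimens "using an asymptotic 2-sided 95% CI for the difference of two independent proportions". The printed formula adds a continuity correction of half of (1/n1 + 1/n2).

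**The concern.** Section 6.5 of the SAP gives two sizes for the same 60-day arm: 260 in Part 1 and 200 in Part 2. The larger figure also disagrees with the SAP's own design section and with the protocol version on which the SAP says it is based.

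The 30-day arm has no justification other than the width of this interval. If the sample size is wrong, the stated precision for the secondary 60-day versus 30-day comparison is wrong too. A reader of the SAP would expect an interval about 20 points wide, and could take a trial that enrolled its planned 300 to be 390 − 300 = 90 subjects short.

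**Working it through.** **Which size is current**

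- SAP 3.1: about 300 at 2:1 gives 200 and 100.
- SAP 6.5 Part 2: 200 × 0.85 = 170, the number stated. Starting from 260 it would be 260 × 0.85 = 221.
- Protocol 10.4: 200 and 100, stated outright.
- SAP 6.5 Part 1: 260 + 130 = 390. No other current section has this total.

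The protocol's change log shows 260/130 in the Amendment 2 text. The SAP's version history dates v2.0 to 16 FEB 2018, before Amendment 7 (protocol Version 8.0, 11 MAY 2018). The printed date of v3.0, 26 JAN 2020, is after it. This explains where the old figures probably come from. The contradiction itself lies wholly in current text.

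**Width of the CI for the difference**

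Half-width = 1.96 × √[p1(1−p1)/n1 + p2(1−p2)/n2]. The SAP's correction adds ½(1/n1 + 1/n2).

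Inputs: p1 = 0.55 (SAP 6.5, protocol 10.4). No 30-day rate is given, so p2 = 0.55 is an assumption. 0.55 × 0.45 = 0.2475.

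*The SAP's own figure, 260/130:* 1.96 × √(0.2475/260 + 0.2475/130) = 0.1047. The correction is ½(1/260 + 1/130) = 0.0058, giving 0.1105.

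*The current design, 200/100:* 1.96 × √(0.2475/200 + 0.2475/100) = 0.1194. The correction is ½(1/200 + 1/100) = 0.0075, giving 0.1269.

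| n (60-day/30-day) | Half-width | Full width | Half-width, corrected | Full width, corrected |
|---|---|---|---|---|
| 260/130 | 0.1047 | 20.9% | 0.1105 | 22.1% |
| 200/100 | 0.1194 | 23.9% | 0.1269 | 25.4% |

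The SAP's 20% is reproduced with 260/130 uncorrected, and the protocol's 0.12 with 200/100 uncorrected. The smaller n widens the interval by a factor of 0.1194/0.1047 = 1.14 uncorrected, and 0.1269/0.1105 = 1.15 corrected.

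**Sensitivity to the 30-day rate**

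With p1 = 0.55 and p2 from 0.30 to 0.65, the 200/100 full width runs from 22.6% to 24.0% uncorrected, and from 24.1% to 25.5% corrected.

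For the uncorrected width at 200/100 to fall to 20%, p2(1−p2) would have to be 100 × [(0.10/1.96)² − 0.2475/200] = 0.1366. That means a 30-day rate of about 16% or 84%.

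**Primary test**

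With the SAP's corrected lower limit, p̂ − 1.96√[p̂(1−p̂)/n] − 1/(2n), the limit first exceeds 16% at:

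- n = 200: 44 cures (0.2200 − 0.0574 − 0.0025 = 0.1601);
- n = 260: 56 cures (0.2154 − 0.0500 − 0.0019 = 0.1635).

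Exact binomial power at a true rate of 55% is above 0.999 for both. The 99% claim survives the change of n.

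**The case against.** The best case on the other side is that this is an editorial slip with no analytic consequence. The success rule for the primary endpoint (lower limit above 16%) and the rule for the regimen comparison (interval excludes 0) use neither the planned n nor the planned width. No estimator, analysis set or missing-data rule changes, and the current protocol already has the right figures. All of that stands, and it limits the weight of the point.

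Several narrower objections also stand:

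- Nothing in SAP 6.5 Part 1 is miscalculated. The width is right for 260/130; the fault is the out-of-date n.
- Setting 25.4% against the stated 20% combines the smaller n, the continuity correction and rounding. The n alone moves the uncorrected width from 20.9% to 23.9%, about 3 points.
- The SAP never states 100 for the 30-day arm. It follows from 300 at 2:1, and only protocol 10.4 gives it outright.
- The Amendment 7 entry mentions a recalculation without numbers, and a footnote in protocol 10.4 still credits its power sentence to Amendment 2. That the size fell to 200/100 at Amendment 7 is an inference, and the point does not need it.
- The 55% for the 30-day arm is the reviewer's assumption.

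None of these removes the contradiction between current sections.

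**Conclusion.** The point holds. SAP 6.5 Part 1 gives a sample size (260/130) and a precision (about 20% full width) that do not belong to the trial described in SAP 3.1, SAP 6.5 Part 2 and protocol 10.4. At 200/100 the full width is about 24% uncorrected, or about 25% with the interval the SAP specifies, given 55% cure in both arms. It stays above 20% for any plausible 30-day rate.

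The consequence is confined to the planning statement. The primary conclusion, its power and the decision rule for the secondary comparison are unaffected. It should still be corrected, because it is a wrong sample size in the governing analysis document and because interval width is the only stated basis for the size of the 30-day arm.

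**What to change.** In SAP 6.5, Part 1:

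1. Replace 260 with 200 in the power sentence. The 99% can stay.
2. Replace 130 and 260 with 100 and 200 in the precision sentence.
3. Replace the 20% full width with a half-width of about 0.12, as in protocol 10.4. Add that it is about 0.13 (full width about 25%) with the continuity-corrected interval of SAP 6.2.1.1. State that both figures assume 55% cure in each arm. The sponsor should confirm that assumption, since neither document gives a 30-day rate.

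The cost is SAP wording only. The design, the analysis and the protocol's 0.12 stay as they are.

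As a separate query, the sponsor should verify that the 55% is a nifurtimox rate, because the title of the reference cited for it names benznidazole. The answer does not affect the correction above.

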## Part 2 (CHICO SECURE)

According to Sosa-Estani [7, 7], the 48 months post treatment cure rate for benznidazole is about 5% as confirmed by two types of assay. For the primary objective, assuming a drop-out rate of 15%, the expected number of patients to be observed at the end of Part 2 (i.e. 48 months post treatment) in the 60-day regimen would be 170 out of the 200 patients in Part 1. Using the assumptions of 170 nifurtimox 60-day regimen patients in Part 2, a 5% cure rate, and that seronegative conversion events follow Poisson distribution, the estimated incidence rate is calculated to be 1.32% and the 95% CI of the incidence rate is (0.61%, 1.51%).

## 7. Document history and changes in the planned statistical analysis

5.	· · · · · · · · · · · · · · · · · · ·	
Version	Date	Action
Version 1.0	21 OCT 2015	Signed initial version
Version 2.0	16 FEB 2018	Signed version 2.0

## Figure 7–1 Version History

**Statistical Analysis Plan** 

BAY No. A2502/IMPACT No. 16027 Page:

Version 3.0 26 JAN 2020 Signed	ned version 3.0
--------------------------------	-----------------

## 9. Appendices

## 9.1 Assessment of Chagas' disease signs and symptoms

Assessments of the presence of Chagas' disease signs and symptoms will be performed during physical examinations at Screening, Visits 3, 6, and 8 (EOT), and Visits 9, 10, and 11 (follow-up) in part 1 and at FU Visits 1, 3, and 5 in part 2 of the study, and will be entered into the eCRF. Signs and symptoms of Chagas' disease include but are not limited to the following:

## Acute Chagas' disease:

• Fever: usually prolonged

- malaise
- lymphadenopathy
- hepatomegaly
- splenomegaly
- subcutaneous edema (localized or generalized)
- signs of portal of entry of T. cruzi:
  - $\circ$  through the skin chagoma
  - o via the ocular mucous membranes Romaña sign
- hypotonicity
- anemia
- myocarditis
- meningoencephalitis
- pneumonitis
- ECG abnormality, may include but not limited to:
  - o sinus tachycardia
  - o first-degree atrioventricular block
  - o low QRS voltage
  - primary T-wave changes
- Chest radiograph abnormality, include variable degrees of cardiomegaly
